3.3 Study Procedures

[figure not shown]

Figure 1– Flowchart of study activities

All of the study team will receive training on the study protocol and other protocol-related procedures prior to study start. At each center, the study will only start after the study protocol and PIVC site assessment training is completed (Figure 1).

Study procedures will be completed in a single center (pilot study site) prior to initiating study activities in the remaining centers. This strategy will allow for the adjustment of any training or monitoring needs identified at the first center. At each study site, including the pilot study site, study activities at the participating wards will be performed in parallel. The Principal Investigator (PI) will be responsible for selecting, at each site:

- The wards that will be audited within the context of this study.
- The healthcare professionals (auditors) that will be responsible for auditing the participating wards. Auditors will be healthcare professionals (e.g. nurse, resident physicians) with extensive experience in PIVC therapy and who are employed by the study site.

Once the PI has selected the hospital's wards that will be participating in the study, the PIVC Therapy Standards of Practice Questionnaire will be completed by him/her or a designee. If there are individual PIVC therapy standards of practice per ward, rather than hospital-wide standards, the PI will interview the ward nurse manager or a ward clinician of the selected wards and complete the PIVC Therapy Standards of Practice Questionnaire for each ward.

To minimize subject selection bias, all subjects will be identified and invited to participate in the study consecutively, as the auditor goes through the ward. An informed consent process will be carried out by the PI, auditor or a designee. After the subject provides his/her written informed consent to participate in the study, data will be collected from the subject's medical records and by observation of the PIVC site. All PIVC sites, regardless of catheter commercial brand, should be assessed. Data on each PIVC site will be recorded on the Individual PIVC Questionnaire.

In addition to collecting general characterization data on the patient and the PIVC, the auditor will be observing the PIVC site for presence of the following complications (see Appendix I for definitions):

- Clinical complications:
 - Phlebitis:
 - According to grade: grade 1-4

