6.2 Statistical Methods

6.2.1 General aspects

For the purposes of the present study, the unit of analysis will be the individual PIVC sites and not the patients in which they are inserted.

Descriptive statistics will be obtained for numerical variables, including central tendency measures such as mean, median as well as the dispersion measures of standard deviation, min-max and inter-quartile range. Descriptive statistics for categorical variables will include frequencies' tabulation with counts and percentages. No imputation of missing values will be made. 95% confidence intervals will be used if applicable. The significance tests of association under exploratory analyses will be made at the 5% significance level.

Data will be presented for the overall study sample, as well by hospital and by hospital ward.

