6.2.4 Exploratory endpoint analyses

Exploratory analyses will be performed with the aim of identifying the subject- and PIVC characteristics associated with the occurrence of PIVC-related complications.

The association of qualitative variables with the occurrence of PIVC-related complications will be performed with the chi-squared test or with the Fisher's test, while the association of quantitative variables with the occurrence of PIVC-related complications will be performed with the student's t test or the Mann-Whitney test.

Generalized estimating equation (GEEs) models will be used to identify the most important patient characteristics associated with the multivariate binary occurrence of PIVC-related complications, with a Logit link function and considering the correlation structure assumed as exchangeable within patients. The Odds Ratios as well as 95% confidence intervals will be estimated. The significance level will be established at 5%.

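### Section 6.2.4 allows for correlation within patients at most, never within wards, so confidence intervals and tests for characteristics that follow the ward will be too optimistic (exploratory, low severity)

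*Combined protocol and SAP*

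**What the plan says.** - **Unit.** Section 6.2.1 states that "the unit of analysis will be the individual PIVC sites and not the patients in which they are inserted".
- **Aim.** Section 6.2.4 aims at "identifying the subject- and PIVC characteristics associated with the occurrence of PIVC-related complications".
- **Univariate tests.** For qualitative variables the association "will be performed with the chi-squared test or with the Fisher's test". Quantitative variables get a t or Mann-Whitney test. No adjustment for clustering is mentioned.
- **Model.** The GEE is "used to identify the most important patient characteristics associated with the multivariate binary occurrence of PIVC-related complications", with a logit link and "considering the correlation structure assumed as exchangeable within patients". Odds ratios with 95% intervals and a 5% significance level are specified.
- **Sampling.** Under section 3.3 the investigator at each site chooses the wards and the auditors for them. The practice questionnaire is repeated by ward "If there are individual PIVC therapy standards of practice per ward, rather than hospital-wide standards".
- **Use of ward.** Section 6.2.1 says "Data will be presented for the overall study sample, as well by hospital and by hospital ward". Ward and hospital appear nowhere as a cluster, random effect or model term.

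**The concern.** Patients on one ward share staff and case mix, possibly a practice standard and possibly the auditor. Their complications may therefore be correlated even when the patients are different people. A GEE clustered on patients treats them as independent, and the univariate tests also treat two catheters in one patient as independent.

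This matters for characteristics that also vary mainly between wards. For these, a difference between wards can be reported as an association with the characteristic, with an interval that looks more precise than it is. Section 1.2 expects the data to help nurses choose products and design training, so a spurious product association could be acted on.

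**Working it through.** **Inputs from the plan.** Three hospitals (3.2) with at least 100 PIVCs each (6.3): 3 × 100 = 300, which reproduces the stated total. Section 6.3 states that no formal sample size calculation was done, so there is no planned standard error or design effect to reproduce.

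**Inputs assumed.** Ward ICC of the outcome ρ_y = 0.02, 0.05 or 0.10; 4 wards per hospital, hence 12 wards and m = 300/12 = 25 PIVCs per ward; two-sided 5% tests.

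**Formulas.** For a covariate with share ρ_x of its variance between wards:

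- DEFF = 1 + (m − 1) × ρ_y × ρ_x
- true SE ÷ reported SE = √DEFF
- actual type I error = 2[1 − Φ(1.96/√DEFF)]

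**Values of ρ_x.**
- Factor fixed by ward: 1.
- Factor used in 10% of PIVCs in half the wards and 90% in the rest: 0.4²/(0.5 × 0.5) = 0.16/0.25 = 0.64.
- Same with 30% and 70%: 0.2²/0.25 = 0.16.
- Patient covariate with a fifth of its variance between wards: 0.20.

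**Example.** Ward-fixed factor, ICC 0.05: DEFF = 1 + 24 × 0.05 = 2.20; √2.20 = 1.48; 1.96/1.48 = 1.32; type I error 19%.

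| Factor | ρ_x | DEFF at ICC 0.02 / 0.05 / 0.10 | SE ratio | Type I error |
|---|---|---|---|---|
| Fixed by ward | 1 | 1.48 / 2.20 / 3.40 | 1.22 / 1.48 / 1.84 | 11% / 19% / 29% |
| 10/90 by ward | 0.64 | 1.31 / 1.77 / 2.54 | 1.14 / 1.33 / 1.59 | 9% / 14% / 22% |
| Patient covariate, 20% between wards | 0.20 | 1.10 / 1.24 / 1.48 | 1.05 / 1.11 / 1.22 | 6% / 8% / 11% |
| 30/70 by ward | 0.16 | 1.08 / 1.19 / 1.38 | 1.04 / 1.09 / 1.18 | 6% / 7% / 10% |
| Unrelated to ward | 0 | 1 | 1 | 5% |

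The number of wards matters as much as the ICC. For a ward-fixed factor the error is 16% / 29% / 42% with 6 wards in total and 7% / 10% / 16% with 30.

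**Check by simulation under no true association.**
- *Exchangeable logit GEE clustered on patients* (prevalence 40%, 15% of patients with two PIVCs, 300 runs per setting). Ward-fixed factor: 11% / 25% / 28% with 12 wards and 8% / 12% / 16% with 30. An 80/20 factor: 5–14%. Patient factor unrelated to ward: 4–8%. Monte Carlo error is about 1.3 points at 5% and 2.6 points at 28%.
- *With hospital terms added* (prevalence 35%, 270 patients of whom 30 have a second PIVC, patient-clustered robust SE, 4 wards per hospital, ICC 0.02–0.10). About 9–30% for a ward-fixed factor, 10–19% for a 10/90 factor and 5–11% for weakly linked factors.

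Formula and simulation agree to within a few points. They show the order of magnitude and are not predictions for this study.

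**Check of remedies.** Clustering the GEE on ward with the ordinary sandwich SE left 7–14% error for ward-fixed factors with 12–30 wards, and gave 6–11% for patient factors unrelated to ward. A small-sample correction is therefore needed. Adding ward as a model term brought the 10/90 factor to about 4–6%.

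**The case against.** **The GEE may not be aimed at ward-linked factors.** Its sentence names patient characteristics. A reader might infer that dressing and connector type are ward-driven factors due to be tested in that model. The documents do not support this. Ward-specific standards are conditional in 3.3. Dressing type, securement, flush solution and inserter are recorded per PIVC in 3.4.1 and are not in the hospital/ward standards list; of the candidate factors, connection method and port caps are. Section 3.4.1 also allows for insertion in the emergency department, operating room, ambulance or another hospital, so a catheter's features need not follow the audited ward. This stands, and it limits the claim to characteristics that do follow the ward. It does not remove the point: if PIVC characteristics are outside the GEE, they are left to univariate tests that ignore both patient and ward.

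**The large figures rest on strong ward links and an assumed ICC.** This also stands. Weak links give about 5–8% at ICC 0.05, and with ICC near zero there is no problem.

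**A ward term is costly.** For a 10/90 factor with 4 wards per hospital, the median SE rose from 0.25 to 0.43 (0.43/0.25 = 1.72). Rejection at a true odds ratio of 2 fell from 74% to 43%, although part of the 74% was the inflation itself. For a complication with an assumed 5% prevalence, some 45–65% of wards would have no events and add nothing. A compulsory ward term is therefore not justified.

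**The analysis is exploratory.** Sections 2.3 and 6.1.3 say so, and ward differences will be visible in the by-ward tables. This sets the severity low, but the plan still commits to 95% intervals and 5% tests, and these should be valid.

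**Conclusion.** The point holds in a limited form. Section 6.2.4 handles within-patient correlation in one model and no clustering in its other tests, while the design samples by ward and anticipates ward-specific practice. Any positive ward ICC makes the stated precision too good for characteristics that follow the ward. The direction is certain under that condition; the size is not.

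With 4 wards per hospital and ICC 0.02–0.10, both assumed, false positives are about 9–30% for a ward-fixed factor, 10–19% for a 10/90 factor (the formula reaches 22%), and 5–11% for weak links. Patient factors unrelated to ward are about right under the planned GEE. Because only exploratory associations are touched, severity is low.

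**What to change.** In 6.2.4:

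1. Take inference for all subject and PIVC characteristics from the logit GEE, and present the chi-squared, Fisher, t and Mann-Whitney results as descriptive only.
2. Account for ward in the GEE in one of two ways, with the rule for choosing fixed beforehand. Where ward numbers allow, cluster on ward with patients nested within it, using a small-sample-corrected robust SE, a t reference and hospital terms. Where events per ward allow, use a ward term and keep the within-patient correlation. Three hospitals are too few to serve as sandwich clusters, so hospital belongs in the model as fixed terms.
3. For a factor constant within every ward, when wards are too few for ward-level inference, report prevalence by ward and factor level without a PIVC-level p-value or interval.

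The cost is a few sentences of analysis text. Ward is already needed for the by-ward tables, but 3.4.1 does not list the audited ward among the individual PIVC variables, so confirm that it is captured. The real downside is wider intervals and less power for ward-linked factors, and under a ward term the loss of wards without events.

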6.3 Sample Size Justification

No formal sample size calculation has been performed. Based on expert knowledge, it is assumed that a minimum of 100 PIVCs audited per hospital (or a total of 300 PIVCs audited in the study) will provide an adequate estimate of the prevalence of PIVC-related complications. In case a site experiences difficulty in meeting the expected recruitment rate, other participating sites may be proposed to include an additional number of patients, until the total is achieved.

6.4 Procedures to Account for Missing, Unused, and Spurious Data

Investigation of spurious and/or missing data will be discussed in the final report. Imputation of missing data will not be performed. Non-use of data will be described and justified in the final report.

6.5 Deviations to Statistical Plan

Any deviation(s) from the original statistical plan should be described and justified in the final report, as appropriate.

7. Monitoring

3M, as sponsor of this study, is responsible for ensuring the proper conduct of the study regarding adherence to the protocol, as well as to the applicable legislation and regulation, and the validity of the data recorded on the eCRFs. Monitoring activities will be performed at the study sites by:

- Periodic on-site review
- Telephone communications
- Review of eCRFs and source documents (e.g. patient hospital records, clinical charts, doctor's notes, Informed Consent Form, etc.)

The Investigator will give the 3M and the CRO study monitor direct access to source documents that support data on the eCRFs and make available such records to authorized 3M personnel, Quality Assurance personnel, Ethics Committee, and regulatory personnel for inspection.

8. Quality Control and Quality Assurance

3M is responsible for implementing and maintaining quality assurance and quality control systems through written standard operating procedures (SOPs) to ensure that this study is conducted, and data are generated, documented and reported in compliance with the protocol, GCP and regulations cited in Section 1.5 of this protocol. Study monitoring will be carried out to accomplish this.

9. Ethics

The study will be conducted in compliance with the protocol, the foundational principles on the Declaration of Helsinki, ICH's GCP and all applicable regulatory requirements.

This research project was prepared in accordance with Resolution No. 466 of December 12, 2012 of the National Health Council, which establishes the ethical standards for research involving human beings. The study will start only after approval of the protocol and of the ICF by the Ethics Committee and after the Research Agreement has been established with the site.

3M must receive a copy of the Ethics Committee approval letter prior to study initiation.

10. Data Handling and Record Keeping

10.1 Study Personnel

Prior to study initiation, the Investigator must provide 3M with a signed investigator agreement (Statement of Investigator). The agreement contains pertinent investigator information (e.g. qualifications, experience, etc.) as well as the Investigator's commitment to conduct the study according to the protocol and all applicable state and federal regulations.

10.2 Pre-Study Documentation Requirements

Prior to study initiation, the Investigator must provide 3M with the following documents:

- Signed protocol including any amendments in place prior to study initiation;
- Curriculum vitae for all study staff;
- Ethics Committee study approval letter;
- Ethics Committee approved consent form;
- Ethics Committee name, location and chairperson;
- Signed research agreement.

10.3 Completion and Return of Case Report Forms (CRFs)

The Investigator will review all eCRFs for completeness and accuracy. If a correction is required, a single line must be drawn through the error. The person making the correction will initial, date, and provide a reason for the error (if not self-evident).

The Investigator must attest to the quality, accuracy and completeness of all eCRFs in a timely fashion. The monitor will review the eCRFs to assure accuracy and completeness. Any data queries prepared after the eCRFs have been completed must be answered promptly.

12.1 Appendix I– Definition of PIVC-related complications

Table A – Definition of clinical PIVC-related complications

Complication	Definition
Phlebitis	
Presence of pain, tenderness, warmth, erythema or streak formation at or near the PIV insertion site due to movement, chemical irritant and/or bacteria. Thus, according to etiology, phlebitis may be classified as:
 
 • Mechanical: If the catheter is dislodged or not secure (i.e., moves) • Chemical: If the patient is receiving, KCl, IV fluids or antibiotics that tend to cause phlebitis • Infective: if local infection is also present 
The degree of phlebitis is rated using a scale ranging from 1 to 4^a:
 
 • Grade 1: Erythema at access site with or without pain. • Grade 2: Pain at access site with erythema and/or edema. • Grade 3: Pain at access site with erythema, streak formation, and/or palpable venous cord. • Grade 4: Pain at access site with erythema, streak formation, palpable venous cord >1 inch in length, and/or purulent drainage.
Hematoma	A localized swelling that is filled with blood caused by a break in the wall of a blood vessel.
Ecchymosis	Similar to a hematoma. A subcutaneous spot of bleeding (from extravasation of blood) with diameter larger than 1 centimeter.
Skin injury	Superficial damage to the skin as seen by redness, tears, or erosion of the skin, or development of blisters in an area exposed to medical adhesive and lasting for 30 minutes or more.
Local infection	Redness and/or induration within 2 cm of exit site with or without purulent drainage.

a. From: Alexander M. Corrigan A. Infusion Nurses Society: Infusion nursing an evidence-based approach. St. Louis, Mo.: Saunders-Elsevier; 2010.

Table B – Definition of mechanical PIVC-related complications

Complication	Definition
Catheter dislodgement	Movement of the PIV catheter out of the insertion site to the point it cannot be safely used, excluding infiltration.
Occlusion	Stopping or slowing of I.V. fluid flowing from the I.V. bag into the bloodstream. Signs: one is unable to easily flush fluid into the catheter without resistance. Causes: blood clotting in the catheter, kinking of the catheter or tubing, an admixture of medications/fluids or a venous thrombosis.
Extravasation	Accidental infiltration of a vesicant or chemotherapeutic drug into the tissues surrounding the IV site resulting in edema and/or tissue necrosis.
Infiltration	When a solution or medication enters the surrounding tissues due to catheter dislodgement or vein ruptures. Recognized by increasing edema at or near the venipuncture site. The degree of infiltration is rated using a scale ranging from 1 to 4: 
 Grade 1: Skin blanched; edema <1 inch in any direction; cool to touch; with or without pain. Grade 2: Skin blanched; edema 1-6 inches in any direction; cool to touch; with or without pain Grade 3: Skin blanched, translucent; gross edema>6 inches in any direction; cool to touch; mild-moderate pain; possible numbness. Grade 4: Skin blanched, translucent; skin tight, leaking; skin discolored, bruised, swollen; gross edema>6 inches in any direction; deep pitting tissue edema; circulatory impairment; moderate-severe pain; infiltration of any amount of blood product, irritant, or vesicant.
Leaking at the infusion site	IV fluid found under the dressing that is exiting the catheter insertion site.

a. From: Alexander M. Corrigan A. Infusion Nurses Society: Infusion nursing an evidence-based approach. St. Louis, Mo.: Saunders-Elsevier; 2010.

Table C – Definition of PIVC-related Quality issues

Issue	Definition
Unstable PIVC	Catheter moves when touched or when patient moves yet is still functioning.
Blood reflux	Blood observed in the tubing, not associated with a recent blood infusion.
Uncontrolled IV infusion rate	Infusion rate controlled by only a roller clamp or by gravity.
Site dressing partially detached	Dressing is lifted off skin, but insertion site not exposed to environment (25% or greater)
Site dressing totally detached	Dressing is lifted off skin and insertion site exposed to environment
Medical tape added to dressing edges	Tape added to the edges of the insertion site cover or dressing to prevent the dressing from lifting up off the skin either due to the presence of edge lift or to prevent lift from occurring.
Unclean dressing	Stains or dirt observed on the dressing due to blood, food, secretions and/or other outside contaminants
Discomfort at the site with or without palpation	When subject states that the catheter is painful or uncomfortable, if asked, OR when subject complains of pain when the catheter insertion site is touched (palpated).
Uncovered tubing access port	An access port that is open to the environment without a cover or cap
Lack of visibility	When the auditor cannot see the catheter insertion site due to (1) the opacity of the dressing, e.g. tape dressing or (2) tape, gauze pad or patch used under a film dressing.

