 - According to etiology: mechanical, chemical, infective
 - Hematoma
 - Ecchymosis
 - Skin injury
 - Local infection
- Mechanical complications:
 - Catheter dislodgement
 - Occlusion
 - Extravasation
 - Infiltration (grade 1-4)
 - Leaking at the insertion site

The PIVC will also be evaluated for the presence of the following quality issues:

- Unstable PIVC
- Blood reflux
- Uncontrolled IV infusion rate
- Site dressing partially detached
- Site dressing totally detached (site exposed to environment)

- Medical tape added to dressing edges
- Unclean dressing
- Discomfort at site with or without palpation
- Uncovered tubing access port
- Lack of visibility at the PIVC site

If the patient has more than one PIVC, one questionnaire will be completed for each PIVC.

Once the wards' audits are concluded, the study-specific electronic case report forms (eCRFs) will be completed by the PI or study designee. The sponsor or sponsor's representative will perform the monitoring activities and, based on the number or type of inconsistencies/ queries raised, the monitor may deem that the site requires additional training. Once the additional training is complete, the audit process will continue with any changes deemed necessary by the monitor to improve the quality and quantity of data collected.

The process of PIVC-related data collection will be repeated at each study site until at least 100 PIVCs have been audited (Table 1).

Table 1 - Study data collection and procedures per audited ward

Study procedures ^a	Pre-audit	Audit day
Completion of hospital's or ward's current PIVC Therapy Standards of Practice Questionnaire ^b	X	
Inclusion and exclusion criteria review		X
Informed consent form signature		X
Completion of Individual PIVC Questionnaires		X

a. Procedures and timeline to be repeated if more than one ward is to be audited at the study site.

b. Repeat survey of current PIVC standards of practice, if the standards are ward-specific.

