 - All patients receiving IV medication, electrolyte or solution
 - ICU patients only
 - Limited to patients receiving specific medications
 - None of the patients
 - Other (specify)
 - Not defined
- Responsible person who adds medications and electrolytes to IV infusion bottles or bags:
 - Nurse
 - Pharmacist
 - Physician
 - Nurse technician
 - Other (specify)
 - Not defined
- Environment where medications and electrolytes are added to IV infusion bottles or bags:
 - Nurses' station
 - Medication room
 - Patient's room/ward
 - Pharmacy
 - Not defined
- Socio-demographic variables:
 - Date of birth
 - Initials
 - Gender

- Individual PIVC variables:
 - Date and time of PIVC audit
 - Date and time of PIVC insertion
 - Responsibility for PIVC insertion:
 - Nurse
 - Physician
 - Nurse technician
 - Other (specify)
 - Unknown/Not documented
 - Department where PIVC was inserted:
 - Emergency department
 - Operating room
 - Intensive or Critical Care Unit (ICU)
 - General ward/clinic
 - Radiology or other procedure room
 - Ambulance/Emergency Medical System (EMS)
 - Other hospital
 - Unknown/Not documented
 - PIVC location:
 - Left or right hand
 - Left or right wrist
 - Left or right forearm
 - Left or right antecubital fossa
 - Left or right upper arm
 - Left or right foot
 - Left or right side of the head
 - Other (specify)
 - Reason for PIVC insertion:
 - IV fluids
 - IV medications
 - Blood sampling
 - Patient unstable/requiring resuscitation
 - Blood product transfusion
 - Parenteral nutrition
 - Chemotherapy
 - Unknown/Not documented
 - Other (specify)
 - Assessment of PIVC site is documented in the patient chart in the last 24 hours: yes, no
 - Site labeled with date and time of catheter insertion: yes, no.
 - Site overdue for relocation: yes, no. If yes: description for absence of relocation in medical records (yes, no)
 - Use of PIVC: continuous, intermittent

- Flush solution used to keep the PIVC open:
 - No flushing
 - 0.9% sodium chloride
 - Heparin/heparinized saline solution
 - Other (specify)
 - Not applicable (PIVC used continuously)
 - Unknown/Not documented
- IV medications and solutions infused using this PIVC within the last 24 hours:
 - Fluids without electrolytes
 - Antimicrobials
 - Analgesics
 - Sedation
 - Other (specify)
 - None
 - Unknown/Not documented
- PIVC gauge/size:
 - 14G (orange)
 - 16G (grey)
 - 18G (green)
 - 20G (pink)
 - 22G (blue)
 - 24G (yellow)
 - 26G (purple)
 - Steel needle
 - Not visible
 - Other (specify)

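### Two Table A rules can misclassify PIVC sites: chemical phlebitis follows the patient's current therapy, and local infection is met by redness alone

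*Combined protocol and SAP*

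**What the plan says.** Section 3.3 has the auditor record phlebitis by grade and also "According to etiology: mechanical, chemical, infective". Appendix I, Table A, defines phlebitis as local signs "at or near the PIV insertion site due to movement, chemical irritant and/or bacteria" and then gives a rule for each type:

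- Mechanical applies when the catheter is dislodged or moves.
- The chemical rule reads "Chemical: If the patient is receiving, KCl, IV fluids or antibiotics that tend to cause phlebitis".
- Infective applies when local infection is also present.

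Local infection is a separate clinical complication in the same table: "Redness and/or induration within 2 cm of exit site with or without purulent drainage".

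On the unit, section 6.2.1 states that "the unit of analysis will be the individual PIVC sites and not the patients in which they are inserted", and section 3.3 adds "If the patient has more than one PIVC, one questionnaire will be completed for each PIVC".

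On exposure, section 3.4.1 collects for each PIVC "IV medications and solutions infused using this PIVC within the last 24 hours". Its levels include "Fluids without electrolytes", antimicrobials, analgesics and sedation, plus a free-text other. None is for KCl or for fluids that contain electrolytes.

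Sections 6.1.2 and 6.2.3 report the prevalence of each specific clinical complication, which includes local infection. No formula calls for a split of phlebitis by etiology.

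**The concern.** The chemical rule is set at patient level and in the present tense, but it labels a single catheter site. Where a patient has more than one PIVC, or an infusion has ended, the label and the site's own exposure can disagree. The plan collects the site-level exposure, but Table A does not refer to it.

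The local infection rule accepts redness near the catheter with no sign of pus. Redness at the access site is also the defining sign of the mildest grade of phlebitis, so one finding fills two complications and triggers the infective type as well.

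What is at stake is the meaning of the etiology breakdown and the size of the local infection prevalence. Section 6.2.1 also presents results by hospital and ward, so differing auditor conventions could look like differences between sites. Sections 1.2 and 3.1 plan to reuse these data as the pre-intervention phase of a pre-post study of a dressing. A baseline that mixes redness with infection would carry into that comparison.

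**Working it through.** The plan gives no figure on this point to reproduce, and section 6.3 reports no formal sample size calculation. The check is of wording, followed by a scale illustration on assumed inputs.

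**1. Chemical rule against the per-PIVC record**

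The rule is read literally, with therapy judged at the audit.

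| Situation | Table A type | Section 3.4.1 item for this PIVC |
|---|---|---|
| Irritant runs only through another PIVC | chemical | no exposure: conflict |
| Irritant ran through this PIVC, stopped less than 24 hours before the audit, nothing listed running now | not chemical | exposure shown: conflict |
| Irritant ran through this PIVC, stopped more than 24 hours before | not chemical | not shown: missed by both |
| Irritant moved from this PIVC to another within 24 hours | chemical | exposure shown: agreement |

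The first two rows are the defect. For KCl, which Table A names, the item shows exposure only through free text.

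**2. Local infection rule against the phlebitis grades**

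- Grade 1 requires erythema at the access site. That is redness within 2 cm, so every grade 1 site meets local infection and hence the infective type.
- Grade 2 is pain with erythema, edema or both. Only sites with erythema meet local infection through redness.
- Grades 3 and 4 end in and/or lists, so it is unclear whether erythema is mandatory. Sites that have it meet local infection.

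**3. Effect on the endpoints**

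Every type counts as phlebitis, so changing the type changes overall phlebitis by 0. Any site that enters local infection through the overlap is already a phlebitis site, and so already has a clinical complication. The counts for at least one clinical complication, for clinical and mechanical together, and for the primary endpoint therefore change by 0. The local infection count does change:

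local infection count = sites qualifying on other grounds + phlebitis sites qualifying only through redness.

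The second term lies between 0 and the number of phlebitis sites.

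**4. Scale, on assumed inputs only**

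The minimum of 300 PIVCs comes from sections 3.7 and 6.3. The other inputs are not in the documents: phlebitis prevalence is assumed at 5% to 20%, and the share of phlebitis sites with the wrong type at 10% to 30%.

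- Type changed, low: 300 × 0.05 × 0.10 = 1.5 sites, or 1.5/300 = 0.5 percentage points of all PIVCs.
- Type changed, high: 300 × 0.20 × 0.30 = 18 sites, or 18/300 = 6.0 points.
- Ceiling on sites added to local infection: 300 × 0.05 = 15 to 300 × 0.20 = 60 sites (5 to 20 points), if every phlebitis site qualified only through redness. The floor is 0.

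**The case against.** The strongest reply is that Table A is not meant to be read so mechanically. The parent definition ties phlebitis to a cause at the insertion site, and Table A says the type *may* be classified in this way. The auditors are experienced and trained (section 3.3). Being on a drug can reasonably include the interval between intermittent doses. The per-PIVC item also lets some stopped infusions be recovered. This stands as a reason to say that the rule *can* mistype a site, not that it does. It does not remove the defect, because nothing tells the auditor or analyst to take the type from that item.

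A reader might infer more than the documents support, in five ways:

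- *Moving an infusion to another PIVC gives the wrong type.* In that case both catheters carried the drug, and calling either site chemical is defensible. The problem is an irritant that ran only elsewhere.
- *All four grades include erythema, so local infection cannot be rarer than phlebitis.* Grade 2 allows edema without erythema, and grades 3 and 4 are ambiguous. That lower bound does not follow.
- *Etiology is a prespecified secondary endpoint.* Section 2.2 asks for clinical complications by type, and section 6.2.3 implements this as each specific complication. Etiology is recorded, but no formula requires it.
- *The plan forbids or fails to allow several etiologies.* The and/or in the parent definition permits more than one cause. The questionnaire itself is not reproduced, so its response format cannot be judged.
- *KCl exposure is lost.* It can be entered as free text.

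**Conclusion.** The point holds in two parts of unequal weight.

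The chemical rule can misassign etiology where an irritant ran only through another PIVC or was stopped before the audit. This touches the recorded etiology and nothing else.

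The local infection rule has more effect. Followed as written, it counts every grade 1 phlebitis site, and any higher-grade site with access-site erythema, as local infection and infective phlebitis. That raises a prevalence the plan reports separately.

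The number of sites affected cannot be derived, because the documents give no phlebitis rate, grade distribution or frequency of multiple PIVCs. The ranges in the working show scale only. The conclusion rests on a literal reading of Table A and on taking the present tense to mean therapy at the audit. The change is worth making before data collection, but the primary result does not depend on it.

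**What to change.** - **Chemical type.** Keep Table A's list of agents and its restriction to those prone to cause phlebitis. Make the condition that they were infused through the audited PIVC within the last 24 hours, matching the item in section 3.4.1. Dropping the restriction would let almost any infusion qualify.
- **Infusate item.** Add a level for KCl and electrolyte-containing fluids.
- **Etiology.** State that more than one type may be marked, and tabulate the combinations.
- **Local infection.** Report local infection and infective phlebitis with and without purulence, which is already on the signs list in section 3.4.1. Also show local infection with and without concurrent phlebitis.

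The cost is one reworded line, one added response level, one marking instruction and a few table rows. Fewer sites will carry a single etiology, and exposure more than 24 hours before the audit will still be missed.
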